### **6.1.3. Post-Treatment Period**

After the last dose (Study Day 50) or last dose for early termination subjects, subjects will return to the clinic once weekly for the first 2 weeks (Study Days 57, 64) and then on Study Days 78, 92, 120, and 141 for safety assessments.

The study site will continue to counsel and ask the subject at each visit if (s)he is maintaining a low sodium diet in the Post-Treatment Period.

All safety data including AEs, in-clinic BP, and concomitant medications will be reviewed by the Sponsor's Medical Monitor or designee on an ongoing basis throughout the trial.

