**PROTOCOL SYNOPSIS (CONTINUED)**

Study Visit Schedule and Procedures (Continued)	
Treatment: Study Days 1 to 50 (Continued) The study site will counsel and ask the subject at each visit if (s)he is maintaining a low sodium diet. The subject is expected to maintain a low sodium diet throughout the study.
 
Subjects that discontinue treatment are encouraged to remain in the study for the Post-Treatment Evaluation Period and will conduct procedures outlined at Study Day 57 visit upon discontinuation of Study Drug.
 
Post-Treatment: Study Days 57 to 141 Subjects are to return to the Study Center for Post-Treatment visits on Study Days 57, 64, 78, 92, 120 and 141.
 
The study site will continue to counsel and ask the subject at each visit if (s)he is maintaining a low sodium diet in the Post-Treatment Period.
 
The final study visit will be Study Day 141 (Week 21).

Primary Endpoint	Percent change in plasma AGT from Baseline to Study Day 57 (Week 9) compared to placebo
Secondary Endpoints	
 
• Change on SBP from Baseline to each scheduled, post-Baseline visit
 
• Change and percent change in plasma AGT from Baseline to each scheduled, post-Baseline visit
 

Safety Endpoint	Incidence and severity of treatment-emergent adverse events (TEAE) (including hypotension and orthostatic hypotension), use of concomitant medications, abnormal findings in laboratory assessments, ECG, and vital signs
Statistical Considerations	

 
Approximately 30 subjects will be stratified based on low Screening ACE/ARB dose or high Screening ACE/ARB dose and randomized in a 2:1 ratio to receive either 80 mg ISIS 757456 or placebo.
 
The primary efficacy analysis will be the comparison of percent change from Baseline to Study Day 57 (Study Week 9) in AGT between ISIS 757456 80-mg group and placebo group.
 
An interim analysis may be conducted after at least 50% of the subjects have been enrolled.

Sponsor	Ionis Pharmaceuticals, Inc.

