SAP	statistical analysis plan
SBP	systolic blood pressure
siRNA	small interfering ribonucleic acid
SC	subcutaneous(ly)
Study Day 1	defined as the first day Study Drug product is administered to the subject
Study Drug	ISIS 757456 or placebo
SUSAR	suspected unexpected serious adverse reaction
TEAE	treatment-emergent adverse event
UACR	urine albumin-creatinine ratio
ULN	upper limit of normal
UPCR	urine protein-creatinine ratio
WBC	white blood cell
WOCBP	woman of child-bearing potential

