## 8.8. Discontinuation of Study Drug

A subject must permanently discontinue study treatment for any of the following:

- The subject withdraws consent
- The subject experiences an AE that necessitates permanent discontinuation of Study Drug

- The subject develops laboratory test abnormalities that meet any of the stopping rules listed in Section 8.6.1 to Section 8.6.5
- The subject experiences an AE that necessitates unblinding of the Investigator

The reason for discontinuation of Study Drug must be recorded in the electronic Case Report Form (eCRF) and source documentation.

For subjects withdrawn for reasons other than withdrawal of consent every effort should be made to complete the early termination of study procedures and observations at the time of withdrawal (see [Appendix A](#)) and ideally within 2 weeks from the last dose of Study Drug.

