#### **9.4.2. Non-Serious AEs**

The recording of non-serious AEs will begin after the subject signs the informed consent form and will stop at the end of the subject's Post-Treatment Period, which is defined as Study Day 141/ Study Week 21. The Investigator will monitor each subject closely and record all observed or volunteered AEs on the AE Case Report Form.

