#### 3.2.2 Subject Population Analyzed

The following analysis populations are defined for this study:

- Full Analysis Set (FAS): All randomized subjects who have received at least 1 injection of Study Drug (ISIS 757456 or Placebo) and who have at least 1 post-Baseline efficacy or exploratory measurements.
- Per Protocol Set (PPS): All FAS subjects who received at least 7 of the 9 doses of Study Drug, did not alter antihypertensive medications during the Treatment Period and prior to Study Day 57, and have no significant protocol deviations that would be expected to affect efficacy or exploratory assessments.
- Safety Set: All subjects who are randomized and receive at least 1 dose of Study Drug.
- Pharmacokinetics (PK) Set: All subjects who are randomized and receive at least 1 dose of ISIS 757456 and have at least 1 evaluable PK sample.

In addition to the above analysis sets, it is recognized that some data displays will be provided for "All Screened", "Screening Failures" and "All Randomized" subjects but no data analysis will be executed in these populations.

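### For subjects who stop drug early, the visit clock is ambiguous and early termination shares the Day 57 visit, so AGT and SBP at true Day 57 are not assured and an on-stop value can be analysed as Day 57

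*Combined protocol and SAP*

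**What the plan says.** Protocol Section 6.1.3 sets the post-treatment timetable in one sentence with two anchors. It opens: "After the last dose (Study Day 50) or last dose for early termination subjects, subjects will return to the clinic once weekly for the first" two weeks, which it names as Study Days 57 and 64, "and then on Study Days 78, 92, 120, and 141 for safety assessments". The Study Glossary ties Study Day 1 to dosing: it is "defined as the first day Study Drug product is administered to the subject".

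Other places that bear on the point:

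- **Protocol Synopsis, visit schedule.** Subjects who discontinue are encouraged to stay for post-treatment follow-up and "will conduct procedures outlined at Study Day 57 visit upon discontinuation of Study Drug".
- **Appendix A.** Treatment early termination and D57 are one column, visit 11, with a window of ±2 days. Footnote 9 assigns the D57 assessments to a treatment early-termination visit.
- **Protocol 6.1.2 and 3.4.3.** Section 6.1.2 sends early stoppers on to the Section 6.1.3 evaluations. Section 3.4.3 lists the same Study Days with no exception for them.
- **Protocol 8.5 and 8.8.** Section 8.5 refers subjects who meet a stopping rule to 8.8 for follow-up. Section 8.8 says that, unless consent is withdrawn, "every effort should be made to complete the early termination of study procedures and observations at the time of withdrawal", ideally no later than two weeks after the last dose. It gives no visit timetable.
- **Protocol 9.4.1 and 9.4.2.** Collection of serious and non-serious events closes at the same point; for non-serious events recording "will stop at the end of the subject's Post-Treatment Period, which is defined as Study Day 141/ Study Week 21".
- **SAP 3.2.1 (Analytical visits) and 3.2.3.** By-visit summaries use the visit label in the data, average results that share a label, and leave out unscheduled results. Missing values are not imputed.
- **SAP 3.2.2 and 3.3.1.** The primary analysis is in the Per Protocol Set (PPS): "All FAS subjects who received at least 7 of the 9 doses of Study Drug", with antihypertensives unaltered before Day 57 and no significant deviations. A Full Analysis Set (FAS) summary is added.

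**The concern.** The primary endpoint is percent change in plasma AGT at Day 57, and SBP is compared at each visit. Both need a measurement at a known time after randomisation. For an early stopper the plan gives two possible dates for each post-treatment visit. It also asks for the Day 57 assessments at the stop, under the visit that completers use for Day 57. Sites could follow different schedules and each be within the text.

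Two things are at stake. First, a true Day 57 value may not be collected, and analysis cannot recover it. Second, the SAP has no rule that places early-termination data by actual day. If the on-stop visit carries the D57 label, its value is analysed as Day 57; if two visits carry that label, they are averaged. The PPS does not fully screen this out, because a subject can stop for good after seven doses and still qualify.

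The end of scheduled safety visits, relative to the stated end of adverse event collection, also depends on which anchor a site uses.

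**Working it through.** **Inputs.** Dosing days 1, 3, 8, 15, 22, 29, 36, 43 and 50 (Protocol 3.4.2). Post-treatment visits labelled 57, 64, 78, 92, 120 and 141 (3.4.3). End of event collection, Day 141 (9.4.1, 9.4.2). PPS minimum, 7 of 9 doses (SAP 3.2.2).

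**The plan's own figure.** 141 − 50 = 91 days = 13 weeks, and 4 + 8 + 13 = 25 weeks. Both agree with Protocol 3.4. The schedule is consistent for a subject whose last dose is on Day 50.

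**Formulas for a last dose on Day L (no dose skipped).**

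- Last-dose clock: actual day = L + (label − 50). The last visit is L + 91, so the shortfall against Day 141 is 141 − (L + 91) = 50 − L.
- Study Day clock: actual day = label, so the shortfall is 0. If the on-stop visit is at L + 7 and Day 57 is not repeated, the wait to D64 is 64 − (L + 7) = 57 − L.

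| Last dose (L) | Doses | Last-dose clock: D57-labelled visit | Last-dose clock: visit on true Day 57 | Last-dose clock: last visit | Days before Day 141 | Study Day clock, Day 57 not repeated: days to D64 |
|---|---|---|---|---|---|---|
| 1 | 1 | 8 | none | 92 | 49 | 56 |
| 3 | 2 | 10 | none | 94 | 47 | 54 |
| 8 | 3 | 15 | none | 99 | 42 | 49 |
| 15 | 4 | 22 | labelled D92 | 106 | 35 | 42 |
| 22 | 5 | 29 | none | 113 | 28 | 35 |
| 29 | 6 | 36 | labelled D78 | 120 | 21 | 28 |
| 36 | 7 | 43 | none | 127 | 14 | 21 |
| 43 | 8 | 50 | labelled D64 | 134 | 7 | 14 |
| 50 | 9 | 57 | D57 | 141 | 0 | 7 |

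**Three readings for an early stopper.**

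1. *Last-dose clock.* No visit labelled D57 is due in the true Day 55–59 window for any L before 50. For L = 15, 29 and 43 a visit falls on true Day 57, but under another label. Visits end 7 to 49 days before Day 141.
2. *Study Day clock, Day 57 treated as already done at the stop.* Nothing is scheduled at Day 57. The wait to D64 is 14 to 56 days, which does not fit weekly visits for the first two weeks.
3. *Study Day clock, Day 57 also held.* True Day 57 values exist and follow-up reaches Day 141. If both visits carry the D57 label, the analysed value is (on-stop + true Day 57) / 2.

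**A PPS-eligible example.** Doses on Days 1, 3, 8, 15, 22, 29 and 36 make seven. On the last-dose clock the visits are Days 43, 50, 64, 78, 106 and 127. With the ±2-day windows, the visits either side of Day 57 cover Days 48–52 and 62–66, so neither reaches Days 55–59. A Day 43 value labelled D57 is 43 − 36 = 7 days after the last dose; the true Day 57 value would be 57 − 36 = 21 days after it. These answer different questions.

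**Weight of one subject.** 30 × 2/3 = 20 and 30 × 1/3 = 10, so one subject is 1/20 = 5% of the active arm or 1/10 = 10% of placebo. This is leverage, not a measured bias.

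**The case against.** The strongest reply is that the third reading is the natural one. Study Days count from first dose, Section 3.4.3 and the Synopsis list Day 57 without exception, and Section 6.1.2 sends early stoppers into a series that starts at Day 57. Footnote 9 says which assessments to do at early termination; it does not say that Day 57 is thereby used up.

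This stands as far as it goes. A reader might infer that both clocks fail and that no AGT or SBP is collected at Day 57 after a stop. The documents do not support that. The third reading collects both. On the last-dose clock, last doses on Days 15, 29 and 43 put a visit on Day 57, and AGT and vital signs are taken at every post-treatment visit. Under Section 8.8 an early-termination visit 14 days after a Day 43 dose would itself fall on Day 57. But no visible text selects the third reading, and its averaging problem remains if both visits carry one label.

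A reader might also infer that safety follow-up is cut short. That holds only on the last-dose clock. Even then 91 days after the last dose are covered, as for completers, and it could be argued that the subject's own post-treatment period shifts with the visits. Sections 8.5 and 8.6 also give event-specific follow-up for liver, renal, platelet, potassium and blood pressure findings.

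Reach into the primary analysis is limited. Subjects with fewer than seven doses are outside the PPS, and some late stoppers would leave it because their antihypertensives were changed. The SAP also calls the outcomes descriptive. Finally, part of the Synopsis and the study schema are not shown and might name a clock, though Section 6.1.3 would still carry both anchors.

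**Conclusion.** The point holds in a limited form. Section 6.1.3 contradicts itself for every early stopper, and the early-termination visit is not distinguished from Day 57. A true Day 57 AGT and SBP measurement is not assured, and the SAP's label rule allows an on-stop value to stand as Day 57 or be averaged with it. The FAS summary and the by-visit comparisons are exposed to any early stopper who remains in the study; the primary PPS analysis is exposed only to those with seven or eight doses who meet the other PPS conditions.

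The effect on labels rests on the assumption that the database follows Appendix A and gives the on-stop visit the D57 label; neither document says so. If it is labelled otherwise and Day 57 is not repeated, the Day 57 value is missing and not imputed. The 7-to-49-day difference in safety visits applies to one clock only and calls for reconciliation, not a finding that follow-up is inadequate. No discontinuation rate is visible, so neither the number of subjects affected nor the bias can be computed.

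**What to change.** 1. **Appendix A and the database.** Give the early-termination assessment its own visit name and label, separate from D57.
2. **Protocol 6.1.2, 6.1.3 and Synopsis.** State that a subject who stops drug but remains in the study still has plasma AGT and seated BP at Study Day 57, counted from Day 1.
3. **SAP 3.2.1.** State that early-termination values are not analysed as Day 57 and are not averaged into it.
4. **Reconcile** the Synopsis, Sections 6.1.2, 6.1.3, 8.5, 8.8, 9.4.1 and 9.4.2, and Appendix A so that one stated clock governs both the post-treatment visits and the event collection window, and the cross-reference in 8.5 leads to that follow-up. Which clock should govern safety follow-up is for the sponsor to settle; the rules for stopping drug are not touched.

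The cost is amendment wording, one extra visit label, and possibly one or a few extra visits per early stopper. With Study Days counted from first dose and Day 57 kept, the shortfall against Day 141 would be zero for every stopping day.

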## **6.2. Laboratory Assessments**

Laboratory analyte samples will be collected throughout the study. A list of these analytes is contained in [Appendix B](#). Blood chemistry should be taken after fasting for at least 8 hours. During this time the subject can drink water and they should ensure that they consume sufficient water in order to not become dehydrated.

If the platelet value, serum creatinine or liver enzyme tests are uninterpretable (e.g., due to clumping, hemolysis or quantity not sufficient) or missing a repeat blood specimen should be re-drawn as soon as possible (ideally within 7 days). Any uninterpretable platelet count result must be rechecked and determined not to have met a stopping rule before dosing can continue. Due to time constraints, a local lab draw is recommended if a repeat blood specimen is necessary to continue dosing at any time after Study Day 1 to Study Day 8. If there is suspicion of EDTA mediated platelet clumping, a repeat platelet count should be collected in a sodium citrate tube as soon as possible.

## **6.3. Restriction on the Lifestyle of Subjects**

### **6.3.1. Contraception Requirements**

All male subjects must refrain from sperm donation and either be abstinent† or use highly effective contraception from the time of signing the informed consent form until at least 13 weeks after their last dose of study treatment.

For male subjects engaged in sexual relations with a WOCBP either the subject or their female partner must use highly effective contraception from the time of signing the informed consent until 13 weeks after the subject's last dose of study treatment.

For the purposes of this study, WOCBP are defined as any female who has experienced menarche, and who does not meet 1 of the following conditions:

- Postmenopausal: 12 months of spontaneous amenorrhea in females > 55 years of age or, in females ≤ 55 years, 12 months of spontaneous amenorrhea without an alternative medical cause and FSH levels in the postmenopausal range for the laboratory involved
- 6 weeks after surgical bilateral oophorectomy with or without hysterectomy
- Post-hysterectomy

For the purposes of the study, highly effective contraception is defined as follows:

For male subjects:

- Highly effective male contraception includes a vasectomy with negative semen analysis at follow-up, or the non-pregnant female partner of WOCBP uses a highly effective contraceptive method (defined below)
- Male subjects with partners that are pregnant must use condoms as contraception to ensure that the fetus is not exposed to the Study Drug

For female partners of male subjects, highly effective female contraception methods comprise:

- Surgical sterilization (e.g., bilateral tubal occlusion), hormonal contraception associated with inhibition of ovulation (combined estrogen and progestogen containing, or progestogen-only), intrauterine contraception device or intrauterine hormone-releasing system

[figure not shown]
†**Note:** Only true abstinence (i.e., refraining from heterosexual intercourse throughout the duration of study participation) is acceptable. Periodic abstinence (e.g., calendar, ovulation, symptothermal, post-ovulation methods), declaration of abstinence for the duration of a trial and withdrawal are not acceptable methods of contraception.

Note: A female condom and a male condom should not be used together as friction between the 2 can result in either or both products failing.

### 6.3.2. Other Requirements

All subjects will be required to fast for at least 8 hours before visits requiring fasted blood sampling.

## 7. STUDY DRUG

## 7.2. Packaging and Labeling

The Sponsor will provide the Investigator with packaged Study Drug (ISIS 757456 or placebo) labeled in accordance with specific country regulatory requirements.

## 7.3. Study Drug Accountability

The study staff is required to document the receipt, dispensing, and return/destruction of Study Drug (ISIS 757456 or placebo) supplies provided by the Sponsor according to Sponsor instruction and in accordance with institutional policy.

## 8. TREATMENT OF SUBJECTS

### 8.1. Study Drug Administration

Blinded vials of Study Drug will be provided by the Sponsor. Vials are for single use only. Study staff blinded to the identity of the drug will administer the Study Drug. Doses of 80 mg will be administered as a single SC injection at the Study Center. Volume to be administered is shown in [Table 4](#). Please refer to the Study Drug Manual provided by the Sponsor for more detailed instructions for Study Drug (ISIS 757456 or placebo) preparation and administration.

**Table 4: Study Drug Dosing Information**

Volume to Administer	Total Dose
0.80 mL	80 mg ISIS 757456 or placebo SC

### 8.2. Other Protocol-Required Drugs

Per eligibility criteria, subjects must be on a stable regimen of 2 to 3 antihypertensives for at least 1 month prior to screening evaluations and will be required to continue the stable regimen throughout the duration of the study (Refer to Inclusion Criteria Section [5.1](#)).

### 8.3. Other Protocol-Required Treatment Procedures

There are no other protocol-required treatment procedures.

### 8.4. Treatment Precautions

There are no treatment precautions required.

### 8.5. Safety Monitoring Rules

Please refer also to the ‘Guidance for Investigator’ section of the Investigator’s Brochure.

For the purposes of the renal and platelet safety monitoring rules, Baseline is defined as:

- The last non-missing measurement prior to the first dose

In addition to the standard monitoring of clinical safety parameters, the following guidelines are provided for the monitoring of selected parameters chosen based on preclinical and clinical observations.

Confirmation Guidance: At any time during the study (Treatment or Post-Treatment Periods), the initial clinical laboratory results meeting the safety monitoring criteria presented below **must be confirmed** by performing measurements (ideally in the same laboratory that performed the initial measurement) on new specimens. All new specimen collections should take place as soon as possible (ideally within 3 days of the initial collection). For stopping rules, if the initial laboratory result is observed during the Treatment Period, the results from the retest **must be available** prior to administering the next dose of Study Drug (ISIS 757456 or placebo).

Re-dosing Guidance: Subjects with initial laboratory test values that reach a stopping rule must not be re-dosed until the re-test results are available. In general, subjects who do not meet the stopping rules based upon retest may continue dosing. However, the Investigator and the Sponsor Medical Monitor (or appropriately qualified designee) should confer as to whether additional close monitoring of the subject is appropriate. If any of the stopping criteria described below (refer to Section 8.6.1 to Section 8.6.5) are met, the subject will be permanently discontinued from further treatment with Study Drug (ISIS 757456 or placebo), evaluated fully as outlined below and in consultation with the Sponsor Medical Monitor or appropriately qualified designee, and will be followed up in accordance with Section 8.8 of the protocol.

#### 8.5.1. Safety Monitoring Rules for Liver Chemistry Tests

The following rules are adapted from the draft guidance for industry, “Drug-Induced Liver Injury: Premarketing Clinical Evaluation,” issued by the U.S. Department of Health and Human Services, Food and Drug Administration, July 2009.

In the event of an ALT or AST measurement that is  $> 3 \times$  ULN at any time during the Study (Treatment or Post-Treatment Period), the initial measurement(s) should be confirmed as described above ideally within 48 to 72 hours. Liver chemistry tests (ALT, AST, ALP, INR, and total bilirubin) should be tested ideally within 48 to 72 hours as well. Additional, confirmatory measurements should also be performed if ALT or AST levels increase to  $5 \times$  ULN.

Frequency of Repeat Measurements: Subjects with confirmed ALT or AST levels  $> 3 \times$  ULN should have their liver chemistry tests (ALT, AST, ALP, international normalized ratio (INR) and total bilirubin) retested 2 to 3 times weekly. The frequency of retesting may decrease to once a week or less until ALT or AST levels become  $\leq 1.2 \times$  ULN or return to baseline levels or Study Drug has been discontinued and the subject is asymptomatic.

Further Investigation into Liver Chemistry Elevations: For subjects with confirmed ALT or AST levels  $> 3 \times$  ULN, the following evaluations should be performed:

1. Obtain a more detailed history of symptoms and prior and concurrent diseases
2. Obtain further history for concomitant drug use (including nonprescription medications, herbal and dietary supplement preparations), alcohol use, recreational drug use, and special diets
3. Obtain a history for exposure to environmental chemical agents and travel
4. Serology for viral hepatitis (HAV IgM, HBsAg, HCV antibody, Cytomegalovirus (CMV), immunoglobulin M (IgM), and Epstein-Barr Virus antibody panel)
5. Serology for autoimmune hepatitis (e.g., antinuclear antibody [ANA])
6. Additional tests may be conducted to rule out:
  - Nonalcoholic steatohepatitis
  - Hypoxic/ischemic hepatopathy
  - Biliary tract disease
  - Hepatitis types D and E

Additional liver evaluations, including gastroenterology/hepatology consultations, hepatic computed tomography (CT) or magnetic resonance imaging (MRI) scans, may be performed at the discretion of the Investigator, in consultation with the Sponsor Medical Monitor. Repetition of the above evaluations should be considered if a subject's ALT and/or AST levels reach  $5 \times$  ULN.

